9.3.2 ANALYSIS OF THE PRIMARY ENDPOINT(S)

We hypothesize that CCT will further increase TCN activation and connectivity. The hypothesis will be tested using 2 (within-subject: pre vs. post) x 2 (between-subject: CBT vs. CBT+CCT) repeated-measures ANOVAs on brain activation and connectivity in TCN.

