4.3 JUSTIFICATION FOR INTERVENTION

The CBT intervention will consist of up to 12 weekly 60 minute sessions of the manualized therapy, adapted from the Coping Cat program, for the treatment of pediatric anxiety disorders. The CBT+CCT intervention will consist of ~30 minutes of CCT games prior to each CBT session, to engage cognitive control capacity prior to receipt of CBT. They may also receive up to 4 weeks of at home CCT to complete for up to two weeks before starting CBT and up to 4 weeks after starting CBT (~30 minutes per session). If assigned, this may be done at home 5 days per week. The CCT games will be designed to target focused attention, response inhibition, working memory and multiple simultaneous attention to constitute a general executive function training, and activate neural systems associated with executive function/cognitive control. Difficulty of the games will be titrated individually and by session to avoid boredom and progressively activate the functional systems underlying cognitive control, which we hypothesize will optimize participant's ability to engage in, and thus benefit from, in the CBT intervention. For both groups, participants will have to complete at least 8 intervention sessions.

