5 STUDY POPULATION

Fifty-four clinically anxious youth will be studied (36 CBT, 18 CBT+CCT). All subjects will be between 7 and 17.99 years old at the time of initial consent. Subjects will be recruited from an existing R01 study at the University of Michigan (HUM00118950, PI [name]), also referred to as parent study. The R01 parent study, at year 4 of the five-year period, has successfully recruited and retained over 100 anxious youth with moderate or greater levels of symptoms, e.g., PARS score > 10 and CGAS score < 60; it will recruit over 100 additional anxious youth randomized 2:1 to CBT and RMT through 05/31/2021. To date, nearly all participants randomized to RMT in the parent R01 study have chosen to continue the CBT sessions after RMT completion; thus we expect 44 youth to be eligible for the CBT+CCT, providing ample opportunity to recruit 36 CBT and 18 CBT+CCT over the one year period of the proposed study. Based on the retention rates of therapy (96.2%) and fMRI motion (89%) in the parent R01, we expect to have 32 CBT-treated and 14 CBT+CCT-treated anxiety youth with usable pre- and post-treatment data.

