9.3 STATISTICAL ANALYSES

9.3.1 GENERAL APPROACH

Data will be analyzed using statistics software such as MATLAB, SPSS and R software. For descriptive statistics, means with standard deviation and range will be computed for continuous data (all brain and behavioral data and some of the clinical data). In general, statistical significance is reported based on $p < 0.05$ two-tailed; for the fMRI data, $p < 0.005$ uncorrected or $p < 0.05$ corrected for family-wise error or false discovery rate where applicable.

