9.3.3 ANALYSIS OF THE SECONDARY ENDPOINT(S)

- (1) We hypothesize that CCT will increase cognitive control capacity (measured by NIH toolbox CC composite scores and behavioral performance on the MSIT task and/or Millisecond scores). The hypothesis will be tested using 2 (within-subject: pre vs. post) x 2 (between-subject: CBT vs. CBT+CCT) repeated-measures ANOVAs on behavioral performance.
- (2) Repeated-measure ANOVAs will be conducted to examine effect of CCT on CBT. We hypothesize that anxiety severity (i.e., continuous PARS score) will be reduced more in CBT+CCT group, relative to CBT group. Chi-square tests will be used to test for differences in the ratio of CBT responders: non-responders between CBT+CCT and CBT group. We hypothesize that CBT+CCT will have more responders than the CBT.

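### The planned ANOVA's group-by-time test pools variances across a 32 vs 14 split, so its error rate depends on an unknown ratio of change SDs; Welch's test is a cheap safeguard

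*Combined protocol and SAP*

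**What the plan says.** Section 9.3.2 tests the primary hypothesis with 2 (pre, post) x 2 (CBT, CBT+CCT) "repeated-measures ANOVAs on brain activation and connectivity in TCN". Section 9.3.3 plans "repeated-measures ANOVAs on behavioral performance" for cognitive control and the same kind of ANOVA for continuous PARS.

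Section 9.3.1 states that "statistical significance is reported based on $p < 0.05$ two-tailed" in general and, "for the fMRI data, $p < 0.005$ uncorrected or $p < 0.05$ corrected for family-wise error or false discovery rate where applicable".

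Section 5 plans 36 CBT and 18 CBT+CCT participants. It then says "we expect to have 32 CBT-treated and 14 CBT+CCT-treated anxiety youth with usable pre- and post-treatment data".

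Sections 9.1 to 9.3.5 name no variance check, unequal-variance test, robust standard error or group-specific variance. Section 9.2 says that no pilot data exist for a power analysis, and no SD of change is given anywhere.

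**The concern.** In a two-group, two-time-point ANOVA, the interaction test uses one variance for both groups' changes. With equal group sizes, a wrong assumption of equal spread does little harm. With a split of more than 2:1 it matters in both directions: the test rejects too often if the smaller group is more spread out, and too rarely if it is less spread out.

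The design does not guarantee equal spread. Section 6.3 says that the comparison is not randomised. The CBT+CCT participants come from the parent study's RMT arm and have already had that course of therapy (section 4.1). Their pre-treatment scan may or may not be repeated when more than about six weeks have passed (section 8.1.3). The amount of training also varies within this group: section 4.3 says of the home training, "If assigned, this may be done at home 5 days per week". That adds spread only if the training affects individuals.

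At stake is the calibration of the p-values and confidence intervals for the primary endpoint and every continuous secondary endpoint. The estimated difference in mean change is the same under either test.

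**Working it through.** **Inputs.** Group sizes are from section 5 and thresholds from section 9.3.1. The SD ratio r (CBT+CCT / CBT) and the effect size d are assumptions, because the documents give neither.

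**1. The plan's own sample figure.** Section 5 bases it on 96.2% retention and 89% usable motion.
- CBT: 36 x 0.962 x 0.89 = 30.8 (stated 32).
- CBT+CCT: 18 x 0.962 x 0.89 = 15.4 (stated 14).
- Total: 46.2 (stated 46).

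Each group is within two participants of the stated number. No single rate gives both exactly (32/36 = 88.9%, 14/18 = 77.8%). The stated 32 and 14 are used below.

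**2. What the planned test is.** Fitting the 2 x 2 model to a simulated data set of 46 participants gave a group-by-time F of 0.3824 on 44 df. The squared pooled t on change scores was also 0.3824.

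**3. Why the level moves.** Take the CBT change SD as 1.
- Variance the pooled test expects: [(31 + 13r²)/44] x (1/32 + 1/14).
- True variance of the difference in mean change: 1/32 + r²/14.

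At r = 1.5 these are 0.1406 and 0.1920, a ratio of 0.732. The critical value of 2.015 then acts like 2.015 x √0.732 = 1.725, which has a two-sided normal tail of 8.5%. This approximation runs low (it gives 4.4% at r = 1), so the level was simulated.

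**4. Simulated type I error.** 32 vs 14, normal changes, equal mean change, 400,000 trials per row:

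| r | Pooled, 0.05 | Welch, 0.05 | Pooled, 0.005 | Welch, 0.005 |
|---|---|---|---|---|
| 0.67 | 2.4% | 4.9% | 0.13% | 0.48% |
| 1 | 5.0% | 5.0% | 0.50% | 0.53% |
| 1.25 | 7.2% | 5.0% | 0.97% | 0.55% |
| 1.5 | 9.3% | 5.1% | 1.58% | 0.55% |
| 2 | 12.6% | 5.0% | 2.76% | 0.53% |

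The Monte Carlo standard error at the 0.05 level is at most about 0.05 percentage points. These are error rates for one test on one summary measure; they do not describe a voxel-wise map with family-wise or false-discovery correction.

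**5. Other splits.** Scan-motion loss does not apply to PARS or the NIH Toolbox, so their split should be nearer the enrolled 36 vs 18. There the pooled test gives 6.9%, 8.6% and 11.1% at r = 1.25, 1.5 and 2 (nominal 0.05). With 46 split evenly, 23 vs 23, it gives between 5.1% and 5.2% at r = 1.5 and 2. The imbalance creates the exposure.

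**6. Cost if variances are equal.** At 32 vs 14 and an assumed d = 0.9, power is 78.5% pooled and 77.0% Welch at 0.05, and 45.0% and 41.5% at 0.005.

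**7. Where Welch falls short.** With strongly skewed (exponential) CBT+CCT changes at 32 vs 14:

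| r | Pooled, 0.05 | Welch, 0.05 | Pooled, 0.005 | Welch, 0.005 |
|---|---|---|---|---|
| 1 | 4.7% | 6.3% | 0.41% | 1.22% |
| 1.5 | 9.4% | 7.5% | 1.59% | 2.00% |
| 2 | 13.3% | 8.1% | 3.35% | 2.44% |

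**The case against.** **The varying training amount does not by itself inflate the error rate.** A reader might infer that optional home training makes the CBT+CCT group more variable and the planned test anti-conservative. If the training does nothing, its amount adds no spread. To reach r by this route with a mean effect of zero, individual effects need an SD of √(r² − 1) times the CBT change SD: 0.75, 1.12 and 1.73 at r = 1.25, 1.5 and 2. That would mean some children gaining and others losing substantially. If the mean effect is not zero, a rejection is not a false positive. This stands.

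**The other sources have no known direction.** A prior RMT course could widen or narrow later change, and the number of therapy sessions varies in both groups. This also stands. Inflation cannot be asserted as fact; at r = 0.67 the planned test is conservative.

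**Welch is not exact.** PARS is bounded at 0 to 30 and some behavioural measures are reaction times and accuracy, so normality cannot be presumed. Under strong skew Welch exceeds its level, and at 0.005 it is worse than the pooled test at r = 1 and 1.5. This limits the claim for the fix. At nominal 0.05 with unequal spread (r = 1.5 and 2), Welch remains the closer of the two.

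**The consequence can be overstated.** A reader might infer that a false-positive result would justify the next grant application. Section 9.2 says that the pilot will supply effect sizes, and the difference in mean change does not depend on the choice of test. Non-random assignment is the larger threat to interpretation, and Welch leaves it untouched.

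The core survives these points: in an unbalanced, non-randomised comparison, the planned test's error rate depends on a quantity nobody knows, and a less sensitive test is readily available.

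**Conclusion.** The point holds as a minor, inexpensive improvement. At 32 vs 14 with normal changes, the planned test's true level at nominal 0.05 runs from 2.4% to 12.6% as the assumed SD ratio goes from 0.67 to 2, while Welch stays at 4.9% to 5.1%. At 0.005 uncorrected, the pooled test reaches about three times nominal at ratio 1.5 and five and a half times at ratio 2.

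These sizes rest on the assumed ratios, on normality, and on a single summary measure per test. The documents do not show that CBT+CCT changes will be more spread out, so they do not support saying that the plan's error rate is inflated. They support saying that it is not controlled against unequal spread in either direction.

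**What to change.** In sections 9.3.2 and 9.3.3, state that the group-by-time effect will be tested with Welch's t-test on change scores. Apply it to region- or network-level TCN summaries, behavioural scores and PARS, each at the threshold that applies under section 9.3.1. Inspect the change distributions for marked skew, and report Welch p-values as approximate where it is present, especially at 0.005.

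A mixed model with group-specific variance is a separate option, not an equivalent one. It can use participants with only one time point, which matters because scans may be skipped at the investigator's discretion (sections 4.1, 4.4 and 8.1.3). If it is preferred, name it instead of Welch, so that one analysis is fixed in advance.

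The cost is a sentence in each section. If variances are in fact equal (assumed d = 0.9, 32 vs 14), power drops by 1.5 percentage points at 0.05 and 3.5 at 0.005. The change does nothing about confounding from non-random assignment, which needs its own treatment.

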9.3.3 ANALYSIS OF THE SECONDARY ENDPOINT(S)

- (1) We hypothesize that CCT will increase cognitive control capacity (measured by NIH toolbox CC composite scores and behavioral performance on the MSIT task and/or Millisecond scores). The hypothesis will be tested using 2 (within-subject: pre vs. post) x 2 (between-subject: CBT vs. CBT+CCT) repeated-measures ANOVAs on behavioral performance.
- (2) Repeated-measure ANOVAs will be conducted to examine effect of CCT on CBT. We hypothesize that anxiety severity (i.e., continuous PARS score) will be reduced more in CBT+CCT group, relative to CBT group. Chi-square tests will be used to test for differences in the ratio of CBT responders: non-responders between CBT+CCT and CBT group. We hypothesize that CBT+CCT will have more responders than the CBT.

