Eighteen RMT subjects in the parent study will be recruited to our CBT+CCT group, and thirty-six age- and gender-matched CBT subjects in the parent study will be recruited to our CBT control group. The proposed study may add:

- 1) For all fifty-four subjects recruited from parent study:
 - a. NIH Toolbox and/or Millisecond behavioral assessment before and after the CBT course of therapy as well as once before the RMT course of treatment and once at about 3 weeks of CBT and another time if completing the fMRI following 4 weeks of at home CCT for the CBT+CCT group
 - b. BRIEF2 questionnaire before, after, and at about week 3 of the CBT course of treatment, as well as once before the RMT course of treatment and at the fMRI following 4 weeks of at home CCT for the CBT+CCT group
 - c. Clinical assessment of anxiety at week 3 of CBT treatment.
- 2) For patients originally randomized to RMT in the parent study who wish to enroll in the current study during their Optional CBT participation:
 - a. augmentation of the CBT offered by the parent R01 study with CCT games delivered prior to each CBT session (CBT+CCT) along with a brief survey (the Self-Assessment Manikin) they may be asked to complete before and after CCT
 - b. fMRI following 4 weeks of at home CCT, and fMRI following CBT+CCT completion
 - c. Clinical measures and assessments before and throughout the course of CBT treatment
 - d. at home CCT (~30 min/day), 5x per week, for up to 4 weeks, for up to two weeks before starting CBT and for up to 4 weeks after starting CBT, along with a brief survey (the Self-Assessment Manikin) they may complete before and after CCT

Data analyses will compare pre- and post-CBT data from the parent study with pre- and post-CBT+CCT data collected for the proposed study. These data will include NIH Toolbox and/or Millisecond measures of behavioral capacity for cognitive control; multi-modal assessment of TCN with fMRI, resting state and DTI; and, detailed assessment of anxiety symptoms using both clinician-interview and self-report. Pre- to post-therapy change in anxiety severity (clinician-measured) will serve as the primary outcome variable; regression analyses will be used to test for associations of anxiety change with changes in brain-behavioral indices of cognitive control following CBT compared to CBT+CCT. To increase clinical relevance of study results, analyses will also consider responder status, a common end point for clinical trials.

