6.4 STUDY INTERVENTION/EXPERIMENTAL MANIPULATION ADHERENCE

Assessments (or subsets of questions from these measures) will mainly be completed as part of the parent study and utilized for analysis in this protocol. At each time point, assessments may include:

Assessments Completed by Independent Evaluator– Weeks 0, 1, 3, 6, 9 & 12

- a) PARS
- b) Clinical Global Impressions-Severity and Improvement Scale (CGI); (*Guy and Bonato 1970*).

Assessments by Clinician – Weeks 1-12

- a) CGI (S/I)
- b) Treatment Adherence Rating Scale (TARS) A therapist-administered instrument to assess patient completion of assigned CBT or RMT homework.
- c) C-SSRS (since last visit)
- d) CGAS

Assessments Completed by Subjects – Weeks 1-12

- a) Medication Adherence (also all fMRIs)
- b) MASC – week 1, 3, 6, 9, 12
- c) CDI – week 1, 3, 6, 9, 12
- d) CGI-I (parent report) – week 3, 6, 9, 12.
- e) FAS (parent report) – week 12
- f) BDI (parent report) – week 12
- g) BAI (parent report) – week 12
- h) Beverage and Food Questionnaire – week 3 and 12
- i) GRIT Scale – week 12
- j) SCARED (parent) – week 1, 3, 6, 9, 12
- k) SCARED (child) – week 1, 3, 6, 9, 12
- l) Life Events Checklist – week 12

Other Assessments

- a) CGAS (Independent Evaluator, Week 0 and 12)
- b) Credibility/Expectancy Questionnaire (CEQ; Subject, week 3) – A 6-item scale rating the patient's expectations for treatment success (Devilly & Borkovec, 2000)
- c) Working Alliance Inventory (WAI; Subject, Weeks 6 & 12) – A 12-item scale rating the patient's feelings about their relationship with the therapist (Horvath & Greenberg, 1989) – approximately 5 minutes.
- d) Randomization “guess” form to be completed by Independent Evaluator at week 12 to assess blinding (CBT-only).
- e) Self-Assessment Manikin (SAM; Subject, may be completed before and after each session of CCT) – A 3-item scale rating the patient's feelings of pleasure, arousal, and dominance (Bradley & Lang, 1994) – approximately 2 minutes.
- f) Behavior Rating Inventory of Executive Function, Second Edition (BRIEF2; Parent, pre-RMT course of treatment, pre- and post-CBT course of treatment as well as week 3 of CBT, and when completing fMRI after completion of 4 weeks at home CCT for the CBT+CCT group) – at 63-item parent-report scale assessing executive function of the patient (Gioia, Isquith, Guy, & Kenworthy, 2015) – approximately 10-15 minutes.

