8 STUDY ASSESSMENTS AND PROCEDURES

8.1 ENDPOINT AND OTHER NON-SAFETY ASSESSMENTS

8.1.1 SCREENING AND INITIAL ASSESSMENTS

Participants will complete questionnaires in order to collect basic health and demographics information. The initial assessment is completed as part of the parent study and will occur in 1 – 3 sessions, depending upon subject convenience. Data collected from this assessment will be used for analysis for this protocol. The following evaluations and assessment tools (or subsets of questions from these measures) may be used to determine eligibility for the study and gather baseline information:

- 1) Demographics and medical history form. An in-house form for basic demographic information, medical and family history completed by study team or as self-report.
- 2) Social Communications Questionnaire (SCQ) (Rutter et al, 2003). A 40-item parent report to rule out diagnosis of Autism Spectrum Disorder.
- 3) Child Behavior Checklist (CBCL), (Achenbach and Rescorla 2001). A 126-item parent-completed checklist which provides DSM-IV oriented subscales for Depressive Problems, Anxiety Problems and Attention Deficit/Hyperactivity Problems (Inattention and Hyperactivity/Impulsivity subscales). Approximately 10 minutes.
- 4) Beck Anxiety Inventory (BAI; Beck & Steer, 1993). This 21-item self-report survey measures severity of anxiety symptoms in adolescents and adults. Approximately 5 minutes.
- 5) Beck Depression Inventory-II (BDI; Beck, Steer, & Brown, 1996). 21-item self-report measure assessing adult depression. Approximately 5 minutes.
- 6) Family Accommodation Scale (FAS; Lebowitz et al., 2012): 13-item parent report measure assessing family accommodation of child symptoms. Approximately 5 minutes.

- 7) Screen for Child Anxiety Related Disorders (SCARED Parent and Child Versions): Developed by [name]., [name]., Marlane Cully, M.Ed., [name]., and [name]., Western Psychiatric Institute and Clinic, University of Pittsburgh (October, 1995). The SCARED consists of 41 items and 5 factors that parallel the DSM-IV classification of anxiety disorders.
- 8) Tanner stage will be determined by self-report on the Pubertal Development Scale (PDS) (Petersen, Crockett et al. 1998).
- 9) Edinburgh Handedness inventory (Oldfield, 1971). A 15-item self-report of hand use.
- 10) State-Trait Anxiety Inventory for Children (STAII-C); (Spielberger, 1973). A self-report, 20-item scale on anxiety symptoms (trait only) for child subjects. Approximately 5-10 minutes.

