9 STATISTICAL CONSIDERATIONS

9.1 STATISTICAL HYPOTHESES

- Primary Endpoint(s): Change in Brain activation and connectivity in the task-control network (TCN)

We hypothesize that **(a)** both groups will have increased activation and functional connectivity in task-control network after therapy vs. before therapy; however, **(b)** the increase will be greater in CBT+CCT vs. CBT only group. Baseline and week 12 assessment will evaluate pre- to post-CBT changes in brain activation and function connectivity in the task-control network including fronto-parietal and cingulo-opercular regions mediating cognitive control. Functional activation and connectivity of these brain regions are assessed using a conflict interference computer task performed during MRI scanning.

- Secondary Endpoint(s):
 - (1) Change in behavioral performance on the conflict interference task and tasks testing cognitive control capacity included in the NIH Toolbox: We hypothesize that **(a)** both groups will have improved behavioral performance on the conflict interference task and tasks testing cognitive control capacity included in the NIH Toolbox; however, **(b)** these effects will be greater in CBT+CCT vs. CBT group. This will be evaluated using two measures of the same construct at baseline and week 12. Pre- to post-CBT changes in the behavioral performance in a conflict interference task will be collected, as well as composite score from tasks included in the NIH toolbox.
 - (2) Change in Pediatric Anxiety Rating Score (PARS): We hypothesize that relative to CBT group, anxiety severity will be reduced more and treatment response rate will be higher in CBT+CCT group. This will be evaluated at baseline and week 12 through the PARS, a 50 question interview-based tool used to assess for the presence and severity of anxiety symptoms in children and adolescents utilizing parental and youth input to guide clinician ratings. The total scores on this scale range from 0 to 30, with scores above 13 indicating clinically meaningful anxiety.

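### The responder comparison is an unadjusted chi-square with no responder rule, between non-randomized groups of which only one has already had RMT, so it can favour CBT+CCT without any CCT effect

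*Combined protocol and SAP*

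**What the plan says.** Treatment response rate is a secondary endpoint (combined protocol and SAP, sections 1.1 and 3). Section 9.3.3 gives the test: "Chi-square tests will be used to test for differences in the ratio of CBT responders: non-responders between CBT+CCT and CBT group". Section 4.1 says that "analyses will also consider responder status, a common end point for clinical trials", and section 9.3.5 uses responder status again in a logistic regression. None of these sections, nor any other, says what makes a participant a responder. Instrument, threshold, reference rating and rater are all unstated.

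Section 9.1 covers severity and response in one bullet: "This will be evaluated at baseline and week 12 through the PARS". It does not say which PARS is baseline for CBT+CCT. The same bullet describes the scale, "with scores above 13 indicating clinically meaningful anxiety". Section 5 describes parent-study participants as having "moderate or greater levels of symptoms, e.g., PARS score > 10 and CGAS score < 60".

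The CBT+CCT group consists of youth first assigned to RMT in the parent study, and section 6.3 says that this study does not randomize. For them, three sets of PARS ratings are relevant:

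- **Before RMT.** The parent-study initial assessment (section 8.1.1) includes PARS and CGI. Its tools "may be used to determine eligibility for the study and gather baseline information", and its data are to be used in this protocol's analysis.
- **After RMT.** There is an RMT week-12 PARS. Section 8.2 permits a repeat before at-home CCT if more than about six weeks have passed.
- **During and after CBT+CCT.** The evaluator's ratings run to week 12 (section 6.4).

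CGI is rated by the independent evaluator and by the clinician, and section 6.4 also lists "CGI-I (parent report) – week 3, 6, 9, 12". No source is named for response, and no reference point is given for improvement.

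**The concern.** A responder count compares two groups fairly only if both start the counted period from a comparable position or the analysis allows for the difference. Here one group has had a prior course of study therapy and the other has not. If RMT lowers PARS at all, on average, the CBT+CCT group starts CBT less anxious.

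How far that matters depends on the missing rule:

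- An absolute week-12 level counts RMT gains whichever rating is called baseline.
- A PARS fall or CGI-I anchored at parent-study entry counts RMT gains directly.
- A percent fall from the pre-CBT rating removes the direct credit. The groups still differ in starting level, and a given percentage is fewer points from a lower start.

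The chi-square has no covariate, so it passes any of these differences through as a group effect. Section 4.1 includes responder status for its clinical relevance, and section 9.2 says that the pilot will supply effect sizes for a later grant application. An inflated difference would carry forward.

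**Working it through.** **Group sizes.** The plan has no power or response-rate figure to reproduce. Its only derivation is the usable sample in section 5, from 96.2% retention and 89% usable motion:

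- CBT: 36 × 0.962 × 0.89 = 30.8 (stated 32)
- CBT+CCT: 18 × 0.962 × 0.89 = 15.4 (stated 14)
- Total: 54 × 0.962 × 0.89 = 46.2 (stated 32 + 14 = 46)

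The total agrees and each arm is within two participants. I use 32 and 14 below.

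**Assumptions, none from the documents except the entry limit.** Entry PARS has mean 17 and SD 4.5, in whole points, truncated to above 10 (section 5). The RMT fall has mean 3 (range 1 to 4) and SD 4. CBT lowers PARS by 30% with noise SD 4, identically in both groups. CCT has no effect. Each group is simulated with 400,000 youth.

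| Quantity | CBT-only | CBT+CCT, RMT fall 3 (range for 1-4) |
|---|---|---|
| PARS 13 or less when CBT starts | 16% | 43% (29-50%) |
| Response = PARS 13 or less at week 12 | 60% | 72% (63-76%) |
| Response = 50% fall from study entry | 21% | 40% (30-46%) |
| Response = 50% fall from pre-CBT rating | 21% | 26% (23-28%) |

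**Hand check for one youth entering at 17, RMT fall 3.** With pre-CBT score S, the week-12 mean is 0.7S.

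- *50% fall from pre-CBT.* Chance = Φ((0.5S − 0.7S)/4) = Φ(−0.05S). At S = 17 this is Φ(−0.85) = 20%. At S = 14 it is Φ(−0.70) = 24%.
- *50% fall from entry, after RMT.* The target is 8.5 and the week-12 mean is 0.7 × 14 = 9.8. The SD is √((0.7 × 4)² + 4²) = √23.84 = 4.88. Chance = Φ((8.5 − 9.8)/4.88) = Φ(−0.27) = 39%.

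Both are close to the simulated averages and show the two mechanisms separately.

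**Effect on the test at 32 v 14, two-sided 0.05, no continuity correction.** With equal rates, the chi-square rejects about 5% of the time. At 21% v 40% it rejects about 29% (12-42% over the range of RMT falls). At 21% v 26% it rejects about 8%, or about 3% with continuity correction.

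**A version without the PARS model.** Let true response be p in both groups, and let a share q of CBT+CCT youth who would not otherwise respond be counted because of RMT gains. Apparent CBT+CCT response is p + q(1 − p). With p = 50% and q = 20%, this is 0.5 + 0.2 × 0.5 = 60%, and the rejection rate is 9.4% (4.9% with continuity correction). For p of 40-60% (section 2.2.1 puts CBT response below 60%), the uncorrected rate is 5.4-6.6% at q = 10% and 10.9-20.1% at q = 30%.

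**Effect of adjustment.** In the same simulation, a logistic model with pre-CBT PARS moves the spurious odds ratio as follows:

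- pre-CBT percent-fall rule: from 1.12-1.44 to about 1.0
- week-12 level of 13: from 1.15-2.13 to about 1.0

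At 32 v 14, about 0.1-0.2% of fits fail. Adjustment cannot be relied on to repair an entry-anchored rule. Of two youth with the same pre-CBT PARS, the one who fell during RMT is already part of the way to the target. The anchor and the covariate are therefore both needed.

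**The case against.** The strongest reply is that the plan already points to the right anchor. Section 4.1 sets pre- and post-CBT data against pre- and post-CBT+CCT data. Section 9.1 explains baseline and week 12 as change from before to after CBT for the primary endpoint, and describes the first secondary endpoint as pre- to post-CBT change. The conditional repeat PARS in section 8.2 makes sense only if the RMT week-12 PARS otherwise serves as the pre-CBT+CCT rating, and section 8.1.3 treats scans the same way. On that reading the missing label is a gap in wording, and the larger gaps in the table describe rules that the plan never adopts. The size also rests on an assumed RMT effect, in an unpowered pilot.

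Much of this stands. Two stronger readings are tempting, and the documents do not support them:

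- A reader might infer that response is judged on a PARS cut of 13. The figure appears only as a description of the scale (sections 8.1.1, 8.2 and 9.1). As a response cut it would also be a poor choice, since youth can enter at 11-13.
- A reader might infer that the CBT+CCT baseline is the pre-RMT assessment. Section 8.1.1 uses the word baseline for the parent-study intake battery. That does not make it the analysis baseline, and post-RMT ratings are planned.

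Nor do the documents say that the parent study has a percentage rule that could simply be adopted.

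The objection does not reach the test itself. With the anchor that the plan favours, the groups would still start CBT at different PARS levels if youth improve during RMT, and the chi-square would still ignore it. Nothing in the plan rules out an absolute week-12 level or an entry-anchored CGI-I.

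**Conclusion.** The concern holds in this limited form. Responder is undefined, the CBT+CCT baseline PARS is implied but not named, and the stated test is unadjusted between non-randomized groups with different treatment histories. If youth improve during RMT, the comparison can favour CBT+CCT when CCT does nothing.

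Under the assumptions above, the bias is small with the anchor that the documents favour (21% v 23-28%). It is large with an entry-anchored rule (21% v 30-46%), and with a week-12 level it is smaller but still material (60% v 63-76%). The direction depends on a mean improvement during RMT. The size depends on assumed figures for the entry distribution, the RMT fall and the CBT fall. Re-anchoring and adjustment deal with the difference in starting PARS. They do not remove prior RMT exposure as a confounder.

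**What to change.** 1. **Section 9.3.3, test.** Make the main responder comparison a logistic regression of response on group, adjusted for pre-CBT PARS. Report the chi-square as support.
2. **Sections 9.1 and 9.3.3, definition.** State the instrument and the threshold before analysis. State that response is rated by the independent evaluator, whom section 6.2.1 describes as blind to assignment. Measure it as change from the last rating before that CBT course. For CBT+CCT that is the RMT week-12 PARS, or the repeat before at-home CCT where done; for CBT-only it is week 0. Say that neither the pre-RMT assessment nor an absolute week-12 level will be used.
3. **CGI-I.** If it contributes to response, name the rater and anchor the rating to the same point.
4. **Consistency.** Use the same baseline wording in sections 4.1, 8.1.1 and 8.2, and the same responder rule in section 9.3.5.
5. **Limitation.** State that prior RMT exposure remains confounded with group.

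The cost is SAP wording and, if CGI-I is used, a short instruction to raters. Most youth need no new data, because the RMT week-12 PARS already exists. The downsides are a slightly less favourable CBT+CCT response figure and a logistic model in a small sample, with an occasional fitting failure for which the chi-square is the fallback.
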